3.3 POPULATIONS FOR ANALYSES

A random cross-sectional sample of parents and caregivers will be selected to participate in a 5–10-minute self-administered survey conducted at 4-week intervals (see Table 3). Prospective parent participants will be identified using a sampling frame provided by schools, at the beginning of the school year, consisting of classroom, classroom size, and grade level. From the sampling frame, three classrooms within each school will be randomly selected. Within the randomly selected classroom, teachers will distribute a survey invitation to all students. Average class size is 25 and we anticipate a 15% response rate per class, resulting in approximately 12 surveys per school or approximately 144 surveys per cluster; equating to 2,880 parent surveys during the 20-week period. Random samples of classrooms will be selected every 4-weeks with replacement using a randomization schedule generated by the study biostatistician, [name]. To increase generalizability, we will randomly select serial cross-sectional samples with replacement since serial samples will allow for greater representation given the likelihood of student absences on the day of recruitment (e.g., potential for individual students to be absent and/or classrooms to be quarantined due to COVID-19 exposure).

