A random cross-sectional sample of parents and caregivers (hereafter referred to as "parents") will be selected to participate in a 5–10-minute self-administered survey conducted at 4-week intervals (see Table 3). Prospective parent participants will be identified using a sampling frame provided by schools, at the beginning of the school year, consisting of classroom, classroom size, and grade level. From the sampling frame, three classrooms within each school will be randomly selected. Within the randomly

selected classroom, teachers will distribute a survey invitation to all students. Average class size is 25 and we anticipate a 15% response rate per class, resulting in approximately 12 surveys per school or approximately 144 surveys per cluster; equating to 2,880 parent surveys during the 20-week period. Random samples of classrooms will be selected every 4-weeks with replacement using a randomization schedule generated by the study biostatistician, [name]. To increase generalizability, we will randomly select serial cross-sectional samples with replacement since serial samples will allow for greater representation given the likelihood of student absences on the day of recruitment (e.g., potential for individual students to be absent and/or classrooms to be quarantined due to COVID-19 exposure). All parents will be notified of the study and the possibility of receiving a survey invitation by school administrators at the beginning of the school year, with periodic reminders.

The primary outcome, diagnostic testing before and after implementation of the SASEA Hub will be examined using a mixed effects logistic regression with fixed effects for Time, SASEA Hub, and the interaction of Time x SASEA Hub. The mixed effects model will include a random component for school-level intercepts (to account for students nested within schools) and district-level intercepts (to account for schools nested in districts). Potential confounders will be controlled for in the model (e.g., baseline COVID-19 diagnostic testing and vaccination rates within communities encompassing schools, school size, race/ethnicity, % receiving free/reduced lunch).

FIDELITY

INTERVENTIONIST TRAINING AND TRACKING

All schools will be receiving the same SASEA Hub website as the intervention with minimal modifications based on their region. Region specific wastewater results and vaccine locations will be provided.

MEASURES TO MINIMIZE BIAS: RANDOMIZATION AND BLINDING

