3.2 SAMPLE SIZE DETERMINATION

Power was computed for a randomized stepped wedge design with 48 schools, 4 clusters (12 schools per cluster), and 5 steps with 1 cluster per step (or 4-week interval) based on diagnostic testing uptake in response to a positive environmental signal (see 1, responsive testing). Power is based on the primary outcome, on-site COVID-19 diagnostic testing uptake in response to a positive environmental signal in schools (see section A.4.1 and C.5.2). Published studies on the uptake of COVID-19 diagnostic testing among school-aged children and their household members in the presence of environmental surveillance are non-existent. We relied on testing rates observed in San Diego County schools during the latter half of the 2020-2021 academic year. Assuming a baseline COVID-19 testing rate of 2%, intra-class correlation $ICC=0.10$, Type I error rate of 0.05, and an average of 500 staff/students per school, we will have more than 80% power to detect a minimal difference of 0.06% in weekly testing uptake (2.0% pre SASEA-SNAP vs. 2.6% post SASEA-SNAP). Using similar assumptions for the secondary outcome, COVID-19 diagnostic testing uptake within household members of students, we will have over 80% power to identify a minimal detectable difference of 2.8% in testing uptake with a serial cross-sectional sample of 2,880 parents (2.0% pre SASEA-SNAP vs. 4.8% post SASEA-SNAP). Power was calculated in STATA 16.1 using a method described by Hemming and Girling

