3.4.2 ANALYSIS OF THE PRIMARY ENDPOINT(S)

Descriptive statistics will be calculated for all primary outcomes, which will be assessed through the collection of weekly diagnostic testing surveillance data (provided by SDHSA) and serial cross-sectional parent surveys. The primary outcome, diagnostic testing before and after implementation of the SASEA program will be examined using a mixed effects logistic regression with fixed effects for Time, SASEA program, and the interaction of Time x SASEA program. The mixed effects model will include a random component for school-level intercepts (to account for students nested within schools) and district-level intercepts (to account for schools nested in districts). Potential confounders will be controlled for in the

model (e.g., baseline COVID-19 diagnostic testing and vaccination rates within communities encompassing schools, school size, race/ethnicity, % receiving free/reduced lunch).

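### Grade level is in the sampling frame, but neither the classroom draw nor the named model covariates use it, so a small and nearly free gain in precision for the Hub effect is left unused

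*Combined protocol and SAP*

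**What the plan says.** The frame supplied by schools at the start of the year is described in the recruitment section, under Administration and/or Dosing, and in section 3.3. Section 3.3 describes it as "consisting of classroom, classroom size, and grade level. From the sampling frame, three classrooms within each school will be randomly selected", and the other two places say the same. The draw is repeated in each round, with replacement across rounds, and no stratification is mentioned.

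The primary model, under Administration and/or Dosing and in section 3.4.2, is a mixed effects logistic regression. It has time, intervention and their interaction as fixed effects, and school and district random intercepts. The potential confounders are given as examples: "baseline COVID-19 diagnostic testing and vaccination rates within communities encompassing schools", then school size, race/ethnicity and the share receiving free or reduced lunch. Grade is not named. Section 3.4.1, where the plan should say whether covariates are pre-specified, still holds template prompts.

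Section 3.4.2 also names "weekly diagnostic testing surveillance data (provided by SDHSA") as a data source for the primary outcomes. It does not say whether the series is by school or by area, or whether it covers weeks before rollout.

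**The concern.** In a stepped wedge trial with fresh cross-sectional samples, each school contributes a comparison of its rounds before and after rollout. If one round happens to draw mostly young classrooms and the next mostly older ones, any difference in testing by grade appears as a change over time in that school. Across schools this averages out, so the estimate stays unbiased, but the extra scatter goes into its standard error. Neither the school intercept nor the time effects remove it, because it varies by school and round together.

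The samples are small: about 11 surveys per school-round as planned, or about 6 if the 971 participants of the Protocol Summary are spread over 26 schools and six rounds. The information needed to remove this scatter is already in the biostatistician's hands when the classrooms are drawn.

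**Working it through.** **Inputs from the documents**
- Design, section 3.2: "randomized stepped wedge design with 48 schools, 4 clusters (12 schools per cluster), and 5 steps with 1 cluster per step", with "intra-class correlation $ICC=0.10$, Type I error rate of 0.05, and an average of 500 staff/students per school".
- Average class size 25, so about 500/25 = 20 classrooms per school.
- Surveys per school-round: 3 × 25 × 15% = 11.25, which the plan takes as 12.
- Alternative size, Protocol Summary: 26 schools, 971 participants, 2-week intervals.

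**Assumptions, not in the documents**
- Three grade bands of 7, 7 and 6 classrooms, and the testing rates by band shown below.
- Six rounds and four waves for the 26-school version, giving 971/(26 × 6) = 6.2 surveys per school-round.

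**Step 1: the plan's own figure.** 12 surveys × 12 schools × 4 clusters × 5 periods = 2,880, as stated. The plan claims over 80% power for a "minimal detectable difference of 2.8% in testing uptake with a serial cross-sectional sample of 2,880 parents (2.0% pre SASEA-SNAP vs. 4.8% post SASEA-SNAP"). I used the generalised least squares variance for a cross-sectional stepped wedge, with categorical time and a school intercept. The covariance of a school's round means is τ²J + (σe²/m)I, where τ² = 0.10σ², σe² = 0.90σ² and m = 12. With σ² = (0.02 × 0.98 + 0.048 × 0.952)/2 = 0.0326, the SE is 0.0112.
- Two-sided, 4 sequences over 5 periods: Φ(0.028/0.0112 − 1.96) = 70.6%.
- One-sided, same layout: 80.5%.
- Two-sided, with the 48 schools spread over 5 steps: 79.5%.

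The stated power is thus reproduced, to within rounding, under standard variants. Sidedness is not stated.

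**Step 2: how uneven the draw can be.** There are C(20,3) = 1,140 possible draws of three classrooms.
- All three bands: 7 × 7 × 6 = 294, and 294/1,140 = 25.8%.
- One band only: 35 + 35 + 20 = 90, and 90/1,140 = 7.9%.

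**Step 3: variance added by grade mix.** If S² is the variance of the band rates over the 20 classrooms, a simple random draw adds (S²/3)(1 − 3/20) to the variance of a school-round mean. For band rates of 2/4/6%, S² = 0.000273, so the added variance is 0.0000772. The sampling variance of the same mean is 0.90 × 0.039 × 0.961/12 = 0.00281. The addition is 2.7% of it.

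**Step 4: effect on the Hub estimate.** The Step 1 variance was recomputed with and without the added term, using the mean band rate for σ² and ICC 0.10.

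| Band rates | Mean rate | Variance fall, 48 schools × 5 rounds × 12 | Variance fall, 26 schools × 6 rounds × 6.2 |
|---|---|---|---|
| 1/2/3% | 1.95% | 1.2% | 0.6% |
| 2/4/6% | 3.9% | 2.5% | 1.3% |
| 5/10/15% | 9.75% | 6.4% | 3.4% |
| 10/20/30% | 19.5% | 13.1% | 7.3% |

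Only the first two rows lie near the plan's 2.0% to 4.8%. At the top of that range, a 2.5% fall in variance is about 1.2% off the SE. On the 70.6% reading, adding the noise back gives Φ(2.503/√(1/0.975) − 1.96) ≈ 69.6%, so about one percentage point of power is at stake.

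**The case against.** A simple random draw of classrooms is valid and unbiased, so this is a refinement rather than an error. That stands. The covariate list is also given as examples, so grade is unnamed rather than excluded. That stands too, although an open list leaves the primary model unsettled and is a reason to name the term. No passage says that testing differs by grade; the Background section speaks only of lower vaccine uptake among children. The three equal bands are assumed, and the planned sites include 8 childcare sites that may not have three grades to sample. Finally, the figures above are on a linear scale. In the planned logistic model a covariate need not shrink the SE of the log odds ratio, and its benefit appears mainly as power for the conditional effect. Balancing the draw removes the chance shift in grade mix whatever the link function.

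A reader might go further and infer that each school's own earlier testing rate is also held, through the weekly county series, and could replace the community rate at no cost. The documents do not support this. They give neither the level of that series nor its coverage before rollout, and they list it as an outcome source. The school-year 2020-2021 rates in section 3.2 are cited for planning, not as a record for each study school. The school intercept and the within-school comparison also do much of the same work: a rate explaining half of the between-school variance would cut the SE by only about 3%.

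**Conclusion.** The point holds as a minor improvement for the survey-based outcomes. Grade is held, the draw and the named covariates ignore it, and using it would remove some chance variation between rounds. The likely size is 0.6% to 2.5% of the variance of the Hub effect. This rests on three similar bands, about 20 classrooms per school, ICC 0.10, a linear scale, and band rates of 1/2/3% to 2/4/6%.

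A reader might infer a reduction of as much as a quarter of the variance by combining the 10/20/30% row with a school-level earlier rate that explains 75% of between-school variance. That needs a mean testing rate of about 20%, against a planned baseline of 2%, and a covariate that the documents do not show to be available. Nor should the point be read as a claim of bias.

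**What to change.** 1. Under Administration and/or Dosing and in section 3.3 (and, for consistency, the recruitment section), stratify each school-round draw by grade band, keeping three classrooms in total: one per band where a site has three bands, otherwise a simple random draw. Define the bands before the first draw.
2. Under Administration and/or Dosing and in section 3.4.2, add grade band as a pre-specified fixed covariate in the primary model.
3. Only if school-level county testing records for the weeks before rollout prove to exist, consider a school's own earlier rate as an addition to the community rate, not a substitute for it. Use it for the survey outcome only, so that the same series is not on both sides of the model.

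Items 1 and 2 cost a small change to the draw program, one model term and the fallback rule. Each response must carry the grade band of its sampled classroom, which is known from the frame. Where bands differ much in size, any descriptive school-level rate should be weighted back to the school's grade mix. No extra classrooms or invitations are needed.

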1 PROTOCOL SUMMARY

Protocol Title	Safer at School Early Alert Hub
Principal Investigator	[name]
Study Sites	University of California, San Diego
Study Activation Date	September 19, 2022
Planned Accrual	Total number of participants - 971
Planned Accrual Period	September 19, 2022 to December 17, 2022
Planned Duration	Data collection period: September 19, 2022 to December 17, 2022 Intervention period: October 3, 2022 to March, 2023
Study Design	Create the Safer at School Early Alert School Hub (SASEA Hub), a school-based environmental surveillance dashboard and diagnostic testing resource hub with an accompanying toolkit for rapid community tailoring to improve COVID-19 testing uptake in vulnerable and underserved communities using a Community Based Participatory Research (CBPR) framework and the Consolidated Framework for Implementation Research (CFIR). We will evaluate the ability of the saseahub.org to increase child and household diagnostic testing uptake via a step-wedge trial, with schools rotated onto the intervention arm (i.e., given access to the saseahub.org) at 2-week intervals. All schools will rotate into the intervention by the Thanksgiving holiday.

Study Objectives	
Aim 1: Create the SASEA Hub, a school-based environmental surveillance dashboard and diagnostic testing resource hub with an accompanying toolkit for rapid community tailoring to improve COVID-19 testing uptake in vulnerable and underserved communities using a Community Based Participatory Research (CBPR) framework and the Consolidated Framework for Implementation Research (CFIR).
 
Aim 2: Assess SASEA Hub's (intervention's) potential to increase diagnostic testing uptake and identify more asymptomatic cases than schools. We will assess this aim through a randomized stepped wedge cluster trial design. The primary outcome will be testing uptake within the past 14-day period, assessed through the SASEA bi-weekly community survey.
 
Aim 3: Assess SASEA Hub's ability to increase risk mitigation behaviors (masking, physical distancing, increased hand hygiene) when the Hub notifies schools of a change in county level COVID-19 case rates or county level wastewater levels

Treatment Description	Intervention – receive access to the community tailored SASEA Hub website
Inclusion Criteria	Parent of a child or staff member attending one of 26 SASEA participating schools

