Exclusion Criteria	All non SASEA school participating individuals or students of SASEA participating schools
Study Outcomes	Primary outcome – The primary study endpoint will be student diagnostic testing uptake in the previous 14-days, measured using household surveys distributed at 2-week intervals.

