END-OF-STUDY DEFINITION

A participant is considered to have completed the study if she or he has completed the community survey.

STUDY POPULATION

INCLUSION CRITERIA

In order to be eligible to participate in this study, an individual must meet all of the following criteria:

1. Parent with children enrolled at any of the 50 schools across the San Diego County that participated in the study during the 2021-2022 school year.
2. School staff working at any of the 50 schools across the San Diego County that participated in the study during the 2021-2022 school year.
3. Provision of signed and dated informed consent form
4. Access to necessary resources for participating in a technology-based intervention (i.e., computer, smartphone, internet access)

EXCLUSION CRITERIA

An individual who meets any of the following criteria will be excluded from participation in this study:

1. Not affiliated with participating sites as parents or staff.
2. No access to necessary resources for participating in a technology-based intervention (i.e., computer, smartphone, internet access)

LIFESTYLE CONSIDERATIONS

N/A

SCREEN FAILURES

N/A

STRATEGIES FOR RECRUITMENT AND RETENTION

This study will consist of a 20-week randomized stepped wedge cluster trial. Parents will be invited to participate in a 5–10-minute self-administered survey conducted at 4-week intervals. Prospective parent participants will be identified using a sampling frame provided by schools, at the beginning of the school year, consisting of classroom, classroom size, and grade level. Between 40 participating schools clustered and 8 childcare sites within 4 district clusters (approximately 12 sites per district cluster) will be enrolled during the study; for a total of 48 sites and 4 district clusters. The average size of school and childcare sites is 500. From the sampling frame, three classrooms within each school will be randomly selected. Within the randomly selected classroom, teachers will distribute a survey invitation to all students. Average class size is 25 and we anticipate a 25% response rate per class, resulting in approximately 20 surveys per site or approximately 150 surveys per cluster. Random samples of classrooms will be selected every 2-weeks with replacement using a randomization schedule generated by the study.

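### The protocol carries two unreconciled schedules, 2-week and 4-week, and the 4-week sampling in section 3.3 cannot yield its five waves or 2,880 surveys in the summary's 90-day collection window

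*Combined protocol and SAP*

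**What the plan says.** **Summary schedule.** The Protocol Summary (section 1) has "schools rotated onto the intervention arm (i.e., given access to the saseahub.org) at 2-week intervals". The primary endpoint is a 14-day recall item "measured using household surveys distributed at 2-week intervals". The summary gives 26 schools, 971 participants, data collection from 19 September to 17 December 2022 and an intervention start of 3 October 2022.

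**Body schedule.** Overall Design (2.4) and Justification for Intervention give 48 sites, 20 weeks and 4-week steps. Section 3.2 computes power for "5 steps with 1 cluster per step (or 4-week interval" and 48 schools. Section 3.3 and Administration and/or Dosing both set 4-week surveys and 4-week classroom draws ("Random samples of classrooms will be selected every 4-weeks with replacement"), about 12 surveys per school and 2,880 in total. Administration dates the 20 weeks from mid-January to early June 2022.

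**Recruitment.** Strategies for Recruitment and Retention contradicts itself. It puts the survey on a 4-week cycle, then says "Random samples of classrooms will be selected every 2-weeks with replacement".

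The amendment history reports a single version, so no later amendment explains the difference.

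**The concern.** These are operating instructions. The biostatistician who draws the classroom schedule and the schools that send out invitations cannot follow all of them, and the choice decides which data exist.

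Two things are at stake. First, the survey total behind the parent-survey power in section 3.2 assumes five waves, which the summary's window cannot hold at 4-week spacing. Second, a stepped wedge draws its information from waves at which some schools have crossed over and others have not. If schools cross every two weeks but are surveyed every four, neighbouring crossover groups look identical in the data and fewer waves contain both conditions.

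**Working it through.** **1. The plan's own total.** 20 weeks / 4 = 5 waves, and 12 surveys x 48 schools x 5 waves = 2,880. This reproduces section 3.3 exactly. (The unrounded yield, 3 x 25 x 15% = 11.25, would give 2,700.)

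**2. Waves in the summary's window.** 19 September to 17 December inclusive is 90 days, or 12.9 weeks.
- 4-week sampling: 19 Sep, 17 Oct, 14 Nov, 12 Dec, so 4 dates or 3 complete intervals.
- 2-week sampling: 7 dates or 6 complete intervals.

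**3. Surveys obtained at 12 per school and wave.**

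| Schools | 4-week (3-4 waves) | 2-week (6-7 waves) |
|---|---|---|
| 26 | 936-1,248 | 1,872-2,184 |
| 48 | 1,728-2,304 | 3,456-4,032 |

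Neither 4-week figure reaches 2,880. The recruitment section assumes a higher yield, about 20 per site. With 26 schools that gives 26 x 20 x 3 = 1,560 to 26 x 20 x 4 = 2,080, still short. Only 48 schools at 20 per site would reach 2,880 in three waves, and that is not section 3.3's yield.

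**4. Body rollout in the summary's window.** Four crossovers at 4-week spacing from 3 October fall on 3 Oct, 31 Oct, 28 Nov and 26 Dec. The last comes after collection closes.

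**5. Exposure patterns if 2-week rollout meets 4-week surveys.** Assume four sequences crossing on 3, 17 and 31 October and 14 November.

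| Survey schedule | Exposure counts from | Distinct patterns | Waves with both conditions |
|---|---|---|---|
| 2-week | crossover or +14 days | 4 | 3 |
| 4-week | crossover | 2 | 1 |
| 4-week | crossover +14 days | 3 | 2 |

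With two patterns, the planned Time x Hub interaction cannot be estimated alongside categorical period effects: for four waves the fixed-effect matrix (4 periods, Hub, Hub x linear time) has rank 5 of 6. It can be estimated if Time is linear or if the 14-day lag applies. The plan does not say how Time is coded.

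**6. Precision of the Hub effect.** Hussey-Hughes variance, school random intercept and fixed periods:

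Var = I s2 (s2 + T t2) / [(I U - W) s2 + (U^2 + I T U - T W - I V) t2]

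Here s2 = (1 - ICC) p(1 - p)/m and t2 = ICC p(1 - p). I is schools, T waves, m surveys per school and wave. U is the number of exposed school-waves. W and V are the sums of squared exposed counts by wave and by school.

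Inputs: I = 26 (summary), split 7/7/6/6 (assumed); ICC = 0.10 and rates 2.0% vs 4.8% (section 3.2), so p = 0.034 and p(1 - p) = 0.03284; m = 12 (section 3.3). Then s2 = 0.9 x 0.03284/12 = 0.002463 and t2 = 0.003284.

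- Four 4-week waves, no lag: U = 66, W = 1,548, V = 174. Var = 26 x 0.002463 x 0.015601 / (168 x 0.002463 + 504 x 0.003284) = 0.000483, SE 0.0220.
- Seven 2-week waves: U = 119, W = 2,673, V = 577. Var = 26 x 0.002463 x 0.025454 / (421 x 0.002463 + 2,106 x 0.003284) = 0.000205, SE 0.0143.
- Ratio 0.0220/0.0143 = 1.54.

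Across 3 or 4 against 6 or 7 waves, with and without the 14-day lag (power: two-sided 0.05):

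| What is held fixed | SE ratio, ICC 0.10 | SE ratio, ICC 0.01-0.10 | Power, 4-week | Power, 2-week |
|---|---|---|---|---|
| 12 per school and wave | 1.31-1.59 | 1.27-1.59 | 23-32% | 48-50% |
| Total of 971 | 0.93-1.18 | 0.87-1.19 | 20-30% | 26-29% |

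Power is for ICC 0.10. For comparison, the same formula applied to section 3.2's design (48 schools, m = 12, 5 periods) gives 70% two-sided, 80% one-sided, and 90% two-sided if the variance uses the 2.0% rate, against the stated figure of over 80%.

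**The case against.** The strongest reply is that section 3.3 is not in error on its own terms. It belongs to the 20-week, 48-school design, where 4-week surveys match 4-week steps and each step already has one wave. The plan for 3-4 weeks of community tailoring before each rotation fits that design too. This stands: a reader might infer that section 3.3 is an isolated slip against a 2-week trial, and the documents do not support that. Most of the body is 4-weekly.

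A reader might also infer that 4-week sampling makes the Hub effect much less precise whatever else is decided. That is not supported either. The 1.3-1.6 ratio takes schools, window and rollout from the summary and the interval and yield from section 3.3, a combination that no single section prescribes. The summary that supplies the 13-week window also plans 971 participants, close to 26 x 12 x 3 = 936. At that total the two schedules are about equally precise, so most of the apparent loss is sample size. The documents do not say whether yield or total is fixed.

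Nor does the Hub effect become inseparable from calendar time. Even with two patterns, one wave has both exposed and unexposed schools, so the main effect remains identified. And 14-day recall every four weeks is no defect in itself, since serial cross-sections need not cover every day.

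What survives is the contradiction, the shortfall in waves and surveys, and the merging of crossover groups if the schedules are mixed. That merging does not depend on the yield.

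**Conclusion.** The point holds as a failure to reconcile two schedules, with consequences for data collection and power. The contradiction and the count of 3-4 waves instead of five follow directly from the documents. So does the shortfall, 936-1,248 surveys against 2,880, given 26 schools and section 3.3's yield.

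The loss of exposure patterns and the precision figures are conditional. They assume four sequences of 7/7/6/6 schools, fortnightly crossovers from 3 October, a first survey on 19 September and the ICC of section 3.2 (lower values are an assumed range). The summary gives only the 3 October start and completion by Thanksgiving. The district intercept was not modelled, and the interaction was checked only for estimability. On these assumptions the SE ratio should be reported as about 0.9-1.6, depending on whether the total or the yield per wave is fixed.

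Redoing the power calculation alone would not settle this, because Recruitment, Administration and section 3.3 would still give conflicting sampling instructions.

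**What to change.** 1. The sponsor should settle one rollout interval, collection window, number of schools and target number, and carry them through the Protocol Summary, Overall Design, Justification for Intervention, the inclusion criteria (which say 50 schools), Recruitment, Administration, 3.2 and 3.3. The documents do not show which schedule is intended.
2. State one sampling rule in Recruitment, Administration and 3.3: one survey wave per rollout step, with classrooms redrawn each wave. This works under either interval.
3. State whether surveys per wave or the total is the planning quantity, and give one response rate (15% and 25% both appear).
4. Say how Time is coded and when a school counts as exposed relative to the 14-day recall.
5. Restate the period count, survey total and power in 3.2 from the reconciled schedule.

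Cost: text edits and one new power calculation. If the 2-week interval is kept, there are more rounds (6-7 instead of 3-4) of a 5-10-minute self-administered survey, which the summary already plans. If 4-week steps are kept, five waves do not fit the 90-day window, so window and step count must be reconciled as well. With 26 schools or 971 participants, the stated power will probably be lower.
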